### **13.3 Statistical Analyses for Aim 2a (Secondary; Effects of IE Intervention on Partner Sexual Function)**

To assess effects of the IE intervention on partner sexual function, which will generally be completed using a male-specific scale (because nearly all partners are expected to be male), we will conduct mixed effects regression analyses (as in Aim 1). Potential same-sex partner sexual function data will be handled in two ways: first, male sexual function as an outcome will be analyzed within the subset of male partners, and second, in exploratory analyses, if possible, we will use clinical cut-off scores across the sexual function scales and using logistic regression models where dysfunctional versus functional status is used as the endpoint, controlling for the effect of partner gender.

### **13.4 Statistical Analyses for Aim 2b (Secondary; Effects of IE Intervention on Patient and Partner Relationship and Psychosocial Outcomes)**

The outcomes in Aim 2b (relationship intimacy and quality, and psychological distress assessed through depressive and anxiety symptom scales) will be assessed using identical measures in both patients and partners. Multilevel modeling (MLM) will be used to test for differences in outcomes between the IE and LHT groups over time. In our primary analysis time, treatment, and role (i.e., patient versus partner) will be treated as categorical with F-tests used to assess mean differences in outcomes. These models include all main effects and interactions among these variables. Models also include random intercepts for patients and partners, as well as the correlation between the intercepts (i.e., if a patient is high in average distress across time, is the partner also high?). Models will include a time-specific correlation between the partners' residuals (i.e., if a patient is distressed at a particular time point, is the partner also distressed at that time?). In addition to modeling the interdependence between patients and partners, MLM has the advantage of not deleting participants with missing data at some time points, thus utilizing all available data.

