### 2.1 Specific Aims

**Specific Aim 1 (Primary Aim):** To evaluate whether the IE intervention will lead to a significantly greater increase in patient sexual function from pre-treatment to post-treatment and 3- and 6-month follow-ups compared to the LHT condition.

**Specific Aim 2 (Secondary Aim):** To evaluate whether the IE intervention will lead to significantly greater improvements in (a) partner sexual function and (b) patient and partner relationship intimacy and quality and psychological distress from pre-treatment to post-treatment and at 3- and 6-month follow-ups, compared to the LHT condition.

**Specific Aim 3 (Secondary Aim):** To evaluate whether increases from pre- to post-treatment in patient sexual communication and self-efficacy for coping with sexual concerns mediate the beneficial effects of the IE intervention on patient sexual function at 3- and 6-month follow-ups.

**Exploratory Aim 1:** To explore whether age ( $\leq 45$  versus  $> 45$  at diagnosis) and race/ethnicity (White versus non-White) moderate intervention effects on the primary outcome of patient sexual function.

**Exploratory Aim 2:** To identify participation barriers and intervention preferences of breast cancer survivors who choose not to participate in the Intimacy Enhancement study.

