#### 4.3 Overview of Randomization and Intervention Conditions

Couples will be randomized with an allocation ratio of 1:1 to either the IE or the Educational Control (Living Healthy Together) condition with stratification by age at diagnosis ( $\leq 45$  vs.  $> 45$ ) using the age obtained from the medical record (or by the patient during screening, if age at diagnosis is not available in the medical record). The statistician ([name]) will generate the randomization sequences using an automated randomization procedure in REDCap that limits prediction of allocation and protects masking of allocations. Randomization in blocks of four will guarantee that after every four assignments the study arms will have equal numbers. Separate randomization tables will be used for FCCC, Duke, and community participants to minimize the potential for unequal randomization by site.

Randomization will occur once both members of the couple have consented, completed baseline surveys, and are scheduled for their first intervention session. Randomization will occur centrally at the primary site by a staff member uninvolved in recruitment (to reduce the potential for bias in randomizing participants onto certain conditions). Once randomized, the couple will be sent sealed study materials along with the instructions to leave the envelopes sealed until they “meet” with their interventionist for session 1. It is important to keep the study condition a secret from participants until Session 1 to reduce the chances for unequal drop-out prior to Session 1, which could occur if patients/partners are more motivated to attend sessions in one study group as opposed to the other.

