### **13.0 Statistical Analysis**

#### **13.1 Overview of Statistical Analyses**

Prior to conducting the primary or secondary analyses, descriptive statistics (i.e., frequencies, measures of central tendency) will characterize the sample in terms of important socio-demographic and clinical characteristics (e.g., age, education, race/ethnicity, and menopausal status) and any other relevant covariates. All outcome variables will be assessed for normality and, if necessary, normalizing transformations may be applied or change scores may be used for outcome measures in analyses. We will describe the interrelationships between all outcomes (primary and secondary) by calculating correlations. To determine whether the enrolled sample differs from eligible study refusers, we will compare these groups on key socio-demographic and clinical factors obtained during screening (e.g., age, treatments) and on severity of sexual concerns using two-sample t-tests or Chi-square tests. Any variables with significant imbalance will be entered in our between groups analyses as covariates. Study completers will also be compared to non-completers on these variables. Every effort will be made to minimize couple drop-out, although some degree of attrition is expected. Logistic regression will be used to understand what factors are predictive of drop-out at the participant level. Factors for possible inclusion in this model include intervention arm, age, level of pre-treatment patient sexual function, and interactions involving intervention arm. Reasons for drop-out will be queried, categorized, and compared within each intervention arm. Our main analyses will account for missing data using multiple imputation with chained equations (MICE). This method will provide valid inferences provided that the probability of having missing data (i.e. drop-out) only depends on the observed data (e.g. treatment arm, baseline sexual function). We chose MICE because it can be used with multi-level models, and it has the ability to readily accommodate categorical variables.

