### **13.2 Statistical Analyses for Aim 1 (Primary Aim; Effects of IE Intervention on Patient Sexual Function)**

The primary analysis will examine whether, relative to the LHT condition, the IE condition leads to greater increases in the primary outcome of patient sexual function at all three post-treatment assessments (T2-4; post-treatment; 3-month FU; 6-month FU). We will also examine specific domains of sexual function (satisfaction, desire, arousal, lubrication, orgasm, pain) separately. In a mixed effects regression model, study condition will serve as the independent variable and patient sexual function at each time point will serve as the dependent variable; pre-treatment sexual function will be included in the model as a covariate with time included as a categorical covariate. Intervention by time interaction effects will be included to test the intervention effect at each follow-up time. Subject-specific random intercepts will account for within-subject variability. Intervention effects on patient sexual function at each follow-up are tested using F tests of combined main and interaction effects.

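### The Aim 2b models in section 13.4 have no stated baseline adjustment, so secondary outcomes are likely to be compared by less precise change-score contrasts

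*Combined protocol and SAP*

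**What the plan says.** Section 13.4 covers four scales (MSIS, DAS-7, PHQ-9, GAD-7), each completed by patients and partners. In the model, "time, treatment, and role (i.e., patient versus partner) will be treated as categorical with F-tests used to assess mean differences in outcomes". On the mean structure it adds: "These models include all main effects and interactions among these variables". The covariance has correlated random intercepts for the two members of the couple and a same-time residual correlation. The section does not say whether pre-treatment (T1) is one of the time levels, and it does not say which F test is the test of treatment.

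The neighbouring sections are more definite. In 13.2 the outcome occasions are T2 to T4, "pre-treatment sexual function will be included in the model as a covariate", and the test is named: "Intervention effects on patient sexual function at each follow-up are tested using F tests of combined main and interaction effects". Section 13.3 takes over that model by reference: "we will conduct mixed effects regression analyses (as in Aim 1".

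Aim 2 in section 2.1 concerns improvement in "patient and partner relationship intimacy and quality and psychological distress from pre-treatment to post-treatment and at 3- and 6-month follow-ups".

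Section 13.1 has a general covariate rule: "Any variables with significant imbalance will be entered in our between groups analyses as covariates". It follows directly on the comparison of enrolled women with eligible refusers. Section 13.1 also allows change scores, as one remedy if outcomes are not normal.

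**The concern.** A full time-by-treatment-by-role factorial contains a treatment main effect, so the arm means at T1 are free to differ. In a randomised trial any difference there is chance. Estimating it and subtracting it in full adds noise that baseline adjustment would largely remove.

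Nothing elsewhere in the plan supplies the adjustment. The rule in 13.1 is triggered by differences between participants and refusers, not by the baseline value of each outcome, and 13.4 has no cross-reference to Aim 1.

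At stake is the width of the confidence intervals for eight comparisons per follow-up (four scales in two roles). The unnamed test adds a second difficulty, because the paragraph can be read as giving different treatment tests with different precision.

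**Working it through.** **Inputs.** From section 13.8: 92 analysable couples at 6 months, two-sided α of 0.05, and for the FSFI an SD of about 10, a change-score SD of 8.2 and a 5-point target difference. From section 4.3: 1:1 allocation, hence 46 per arm. The documents give no SD, correlation or target effect for the Aim 2b scales, so ρ and the effect sizes below are assumptions.

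**The plan's own figure.** For Aim 1 the standard error of a difference in change is 8.2 × √(2/46) = 1.71, and 5/1.71 = 2.92. Power is 83.3% by the normal approximation and 82.5% by the noncentral t with 90 df. The stated 82% is reproduced. Section 13.8 applies 24% attrition to 120 couples: 120 × 0.76 = 91.2, against 92 stated.

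**Correlation implied for the FSFI.** With equal SDs at both times, ρ = 1 − 8.2²/(2 × 10²) = 0.664. If the follow-up SD s differs, ρ = (10² + s² − 8.2²)/(2 × 10 × s), which gives 0.605 at s = 8 and 0.737 at s = 12.

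**Variance of a single follow-up contrast.** Take SD 1, equal correlation between occasions and complete data. The per-arm variance is 2(1 − ρ) for change and 1 − ρ² with own-baseline adjustment. The ratio is 2/(1 + ρ), the ratio of interval widths is √(2/(1 + ρ)), and 92 couples analysed by change have the precision of 92(1 + ρ)/2 couples analysed with adjustment. Power is by the normal approximation at 46 per arm.

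| Assumed ρ | Change | Adjusted | Variance ratio | CI width ratio | Equivalent couples | Power at 0.5 SD, change / adjusted | Power at 0.3 SD, change / adjusted |
|---|---|---|---|---|---|---|---|
| 0.5 | 1.000 | 0.750 | 1.333 | 1.155 | 69.0 | 67% / 79% | 30% / 38% |
| 0.664 | 0.672 | 0.559 | 1.202 | 1.096 | 76.5 | 83% / 89% | 42% / 49% |
| 0.8 | 0.400 | 0.360 | 1.111 | 1.054 | 82.8 | 97% / 98% | 62% / 67% |

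At ρ = 0.3 the standard error from change would be 24% larger than the adjusted one.

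**Check in the dyadic model.** Exact generalised least squares variances were computed for two roles, four times and two arms, with correlated intercepts and same-time residual correlation. At 60 per arm and ρ = 0.664, the treatment-by-time contrast with free T1 means has standard error 0.1497, exactly the change-score value. Constraining the T1 arm means to be equal lowers it to 0.1365, a variance ratio of 0.832 = (1 + 0.664)/2. Varying the patient–partner correlations moves that ratio only between 0.828 and 0.832.

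**Other readings of 13.4.**

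- If time covers only T2 to T4, baseline is not used at all. The variance relative to an adjusted contrast is then 1/(1 − ρ²): 1.33, 1.79 and 2.78 at the three values of ρ.
- If T1 is a level of time and the combined main-plus-interaction test of 13.2 is carried over, complete data give the same follow-up-only comparison.
- If the treatment main effect averaged over all four occasions is tested, a constant follow-up effect is diluted by a quarter, since no effect can exist at T1.
- For change averaged over the three follow-ups, the ratio to the adjusted version is 4/(1 + 3ρ): 1.60, 1.34 and 1.18.

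**The case against.** The strongest reply is that this is a valid analysis. Aim 2 asks about improvement from pre-treatment, a treatment-by-time contrast estimates exactly that, and the plan accepts change scores elsewhere: 13.1 permits them and 13.8 sizes the trial on them. Aim 2b is a dyadic model, and no passage promises the same baseline handling in every section. All of this is true, and it is why the point concerns efficiency and not error. It gives no reason to prefer the less precise estimator: baseline adjustment answers the same randomised question and fits within the dyadic covariance structure.

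A second reply is that the 2/(1 + ρ) figure depends on T1 being a level of time, which 13.4 does not state. That condition stands. The other readings do not rescue the section, however, because they use the baseline less or dilute the effect.

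A third is that the size is not anchored in these outcomes. The value 0.664 comes from one patient scale, the effect sizes are illustrative, and the calculation assumes complete data although 13.1 plans multiple imputation and 13.4 uses partial responders. This also stands. The figures show a range, not a prediction, and the loss becomes small as ρ approaches 1.

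**Conclusion.** The concern holds. As written, 13.4 has no baseline covariate, no equal-baseline constraint and no named treatment contrast. With T1 as a level of time, the follow-up contrasts are change-score contrasts, and they are less precise than adjusted ones for any ρ below 1. Under equal SDs, equal correlation between occasions and complete data, intervals are about 15%, 10% and 5% wider at ρ of 0.5, 0.66 and 0.8. The actual size for MSIS, DAS-7, PHQ-9 and GAD-7 cannot be fixed from the documents. Because couples are randomised there is no bias. Aim 1, its power and the sample size are untouched. The change is worth making because it is free, even though the gain is modest.

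**What to change.** In 13.4, keep the dyadic covariance structure, state how T1 enters the model, and choose one of these in advance:

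1. Model T2 to T4 as outcomes with each person's own baseline score as a covariate, allowing its slope to differ by role. This matches 13.2.
2. Keep T1 as an outcome and constrain the arm means to be equal at T1 within each role.

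The two are close but not identical when the partner's baseline carries extra information. Their variances differed by 0% to 4% over intercept correlations of 0.1 to 0.6 and residual correlations of 0 to 0.4.

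Name the treatment contrasts at the follow-ups as the test, as 13.2 does.

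The cost is a few sentences in the analysis plan. Section 4.3 states: "Randomization will occur once both members of the couple have consented, completed baseline surveys". The scores therefore already exist for both partners, and few or no couples should be lost to missing baselines.

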### **13.5 Statistical Analyses for Aim 3 (Secondary; Mediators of IE Effects on Patient Sexual Function)**

To evaluate whether changes in either sexual communication and/or in self-efficacy for coping with sexual concerns mediate treatment effects on sexual function for patients in the IE condition at 3- and 6-month follow-up, we will use the causal inference framework for mediation described by VanderWeele and others to evaluate whether change (increase) in the mediator variable from pre-treatment to post-treatment mediates improvement (increase) in patient sexual function. Initial models will look for mediation at 3-month follow-up; if evidence of mediation is found, we will also test mediation models which include 6-month follow-up. Effects will be estimated via structural equation modeling, and covariates (age, race, etc.) will be included to account for possible mediator/outcome confounding. Separate models will be fit for the two proposed mediators.

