### **4.2.3 Self Report Measures**

#### **4.2.3.1 Primary Outcome Measure (Primary Aim)**

Patient Sexual Function. Patients will complete the primary outcome measure, i.e., the 19-item Female Sexual Function Index (FSFI), at all four time points (T1-T4). The FSFI is a widely used sexual function measure with established validity in breast cancer. The FSFI is an optimal primary outcome measure because it is comprehensive and multi-dimensional, in that it assesses biological, psychological, and social dimensions of women's sexual experiences including desire, arousal, pain, and satisfaction with sexual relationship, all of which may change due to participation in the IE intervention. Further, in our breast cancer pilot trial, we found a very large effect size for patient sexual function (Cohen's  $d=1.30$ ). The total score will be used as the primary endpoint as it reflects women's overall sexual

function. In addition, we will conduct separate models for each sexual function domain as a supplemental analysis to clarify which domains of sexual function may be driving any effects on overall function. FSFI scores are sensitive to increases in response to participation in behavioral (non-medical) intervention trials in women with cancer up to the proposed 6-month time point.

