#### **4.2.3.3 Mediators (Aim 3)**

Patient and Partner Sexual Communication. Sexual communication is assessed through a brief 6-item version of the Dyadic Sexual Communication Scale (DSCS). The DSCS assesses the quality of communication in a couple's intimate relationship specifically related to sex that has been used successfully in cancer studies. The original scale has 13 items. However, with the aim of reducing participant burden we conducted several analyses including item response curves and correlational analyses to determine whether a shorter version of the DSCS would be valid without losing information. These analyses suggested items 2, 3, 4, 10, 11, and 12 provided 95% correlation with the larger scale. Thus we will use these items in place of the larger scale. Patient and Partner Self-Efficacy for Coping with Sexual Concerns. Self-efficacy for coping with sexual concerns is assessed through three items measuring participants' confidence in their ability to deal effectively with sexual concerns, communicate effectively about sexual concerns, and enjoy sexual intimacy despite physical limitations. These items were developed using standard methods for constructing self-efficacy scales according to social cognitive theory for the IE colorectal cancer study and have high internal consistency as a single scale (Cronbach's alpha=.91). Items use a 0-10 rating scale and reference the past week.

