#### **4.2.3.4 Moderators (Exploratory Aim), Covariates and Other Measures.**

The moderators of patient age and race/ethnicity will be assessed using medical records and pre-treatment self-report survey, respectively. Covariates. Other socio-demographic characteristics (i.e., education, sexual orientation, marital and work status, income, relationship length) will be assessed through self-report. Medical comorbidity for patients and partners will be obtained by a validated self-report comorbidity measure (Self-Administered Comorbidity Questionnaire, SCQ). In order to reduce participant burden and prevent distress, we have modified this measure for patient participants by removing the item asking whether the participant has cancer. We will keep this item for partner participants. Clinical patient characteristics (e.g. menopausal status, comorbidity, types of treatments) will be obtained through medical chart review. Other Measures. We will collect data on frequency of patient sexual activities and use of sexual aids assessed with items from the PROMIS Sexual Function

measure. We also include two items that we developed and assessed in a prior prospective study in colorectal cancer that assess the extent to which sexuality is important to the individual, based on a theoretical model of flexible coping developed by the PI. We are also including the SexFlex Scale, which is a 6-item scale measuring sexual script flexibility when coping with sexual problems. To assess intervention acceptability, at post-treatment (T2), all participants will complete the CSQ-8 and additional questions assessing ease and helpfulness of participation and therapeutic rapport. Based on Borkovec's research, an intervention credibility measure ("Program Evaluation Form") will be completed after session 1 and again at the post-intervention assessment. All participants will complete surveys after session 1, 2, and 3, and again at the post-intervention survey assessing engagement with the material between sessions ("Materials Review Form"). Lastly, we have included a Coronavirus Impact Scale at baseline and six month follow-up to assess the effects the coronavirus pandemic has had on couples' lives, including their relationship and intimacy.

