#### 4.4.3 Developmental Self-Report Survey Data (Exploratory Aim 2)

All data collected from participants in Exploratory Aim 2 (developmental survey study) will be collected using the Developmental Survey, which will be administered verbally using a standardized interview format. This verbal survey collects information on patients' reasons for lack of interest in participating, preferences for resources or programs addressing sexual/intimacy concerns, relationship length/quality, level of confidence in coping with sexual concerns, and race/ethnicity. In addition, if patients endorse the item from the screening script with regard to keeping their information from the screening, we will enter these information (e.g., age, breast cancer data) into our de-identified research files for further descriptive information about this sub-sample.

Table 2. Outcome Measures		Construct	# Items	Baseline	Session 1	Session 2	Session 3	Session 4	Post-Treatment	3-Month Follow-Up	6-Month Follow-Up
Measure											
Primary Outcome											
Female Sexual Function Index (FSFI)* 		Patient Sexual Function	19	X					X	X	X
Secondary Outcomes											
Female Sexual Function Index (FSFI)  International Index of Erectile Function (IIEF) 		Partner Sexual Function	19/15	X					X	X	X
Female Sexual Distress Scale-Revised (FSDS-R)*		Sexual distress	13	X					X	X	X
Miller Social Intimacy Scale (MSIS) 		Relationship Intimacy	17	X					X	X	X
Dyadic Adjustment Scale-7 item (DAS-7)		Relationship Quality	7	X					X	X	X
Patient Health Questionnaire-9 item (PHQ-9) 		Distress (depression)	9	X					X	X	X
Generalized Anxiety Disorder 7-item (GAD-7) 		Distress (anxiety)	7	X					X	X	X
Mediators											
Dyadic Sexual Communication Scale (DSCS) 		Sexual Communication	6	X					X		
Beliefs (self-efficacy) 		Self-Efficacy	7	X					X		
Additional Measures											
Demographic information for patient/partner		Demographic data	13/9	X							
Follow-up demographic/medical questions*		Changes to marital status/medical history	2							X	X
Self-Administered Comorbidity Questionnaire (SCQ) 		Medical comorbidity	14/15	X							

Sexual Self-View	Importance of Sexuality to Self	2 BL/ 1 FU	X					X	X	X
SexFlex Scale 	Sexual Script Flexibility	6	X					X		

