### **13.8 Power Calculations**

Power calculations are based on Aim 1 (Primary Aim). On the patient sexual function measure, a change of 5 points would be considered clinically meaningful (scale range: 2-36,  $SD \approx 10$ ). Based on pilot data, we anticipate that the  $SD$  of the change scores will be 8.2. Using our prior IE trials to guide attrition estimates, we estimate an attrition rate of 24% at 6-month follow-up, resulting in data available from 92 analyzable couples at 6-month follow-up. We will therefore have 82% power to detect a difference of 5 points in change scores, assuming a 2-sided test with type-I error ( $\alpha$ ) of 0.05. In our breast cancer pilot study, we found a between-groups difference in change scores on patient sexual function of 10.7 at post-treatment. Based on results of similar trials, we expect some attenuation of effects by 6-month follow-up. This study is powered to detect a clinically meaningful change  $> (.5 * \text{main effect})$  through the final assessment point. In sum, the study is conservatively powered to detect an effect of the IE intervention approximately half the size obtained in the pilot trial. The sample size of 120 couples (240 participants) was selected based on these calculations.

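### Aim 3 re-measures the mediators only at the survey that also collects post-treatment FSFI and commits to no adjustment or sensitivity analysis for it, so a significant indirect effect would not establish direction

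*Combined protocol and SAP*

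**What the plan says.** Section 13.5 defines the mediator as a change score and the aim as "to evaluate whether change (increase) in the mediator variable from pre-treatment to post-treatment mediates improvement (increase) in patient sexual function". Estimation is by structural equation modeling within a causal mediation framework, with a separate model for each mediator. On confounding it says only that "covariates (age, race, etc.) will be included to account for possible mediator/outcome confounding". On timing: "Initial models will look for mediation at 3-month follow-up; if evidence of mediation is found, we will also test mediation models which include 6-month follow-up".

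Table 2 marks sexual communication and self-efficacy at baseline and post-treatment only. It marks the FSFI at baseline, post-treatment, 3 months and 6 months. The surveys between baseline and T2 (section 4.2.3.4: "All participants will complete surveys after session 1, 2, and 3, and again at the post-intervention survey") concern engagement with the material, and a credibility form follows session 1. Neither carries the mediator scales, so no mediator value after baseline precedes T2 FSFI.

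Section 4.2.3.3 says the self-efficacy items cover confidence to deal with sexual concerns, to communicate about them, "and enjoy sexual intimacy despite physical limitations". Section 13.8 reports that in the breast cancer pilot "we found a between-groups difference in change scores on patient sexual function of 10.7 at post-treatment".

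**The concern.** The mediator does precede the 3- and 6-month outcomes. Nothing, however, orders it against the FSFI change that has already happened by T2, because both changes come from the same two surveys.

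Suppose IE improves function during the four sessions, better function raises confidence and eases communication, and function then persists to 3 months. T2 FSFI would then be a common cause of the T2 mediator and 3-month FSFI. A model without it credits the mediator with an effect it does not have. The reverse path is plausible from the items themselves, since one asks about confidence in enjoying intimacy. Adjusting for baseline FSFI and the baseline mediator does not close this path.

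Aim 3 and Hypothesis 3 are directional: they say these mediators carry the benefit. A positive 3-month result also opens the 6-month models, so an error at the first step carries forward.

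**Working it through.** **1. The plan's own figures.** The documents give no figure for Aim 3. For Aim 1, 120 × (1 − 0.24) = 91.2, stated as 92, or 46 per arm. The standard error of the difference in change is 8.2 × √(2/46) = 1.71, and 5/1.71 = 2.92. Power is Φ(2.92 − 1.96) ≈ 83% by the normal approximation and 82.5% by the t-test (82.1% with 45.6 per arm). The stated 82% is reproduced. The pilot effect is 10.7/8.2 = 1.30 SD of change, which matches the pilot effect size in section 4.2.3.1.

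**2. Inputs.** From the documents: FSFI SD 10, SD of change 8.2, 92 couples, 1:1 allocation, two-sided 0.05, and T2 effects of 5 points (powered) or 10.7 points (pilot). These give a baseline–T2 correlation r = 1 − 8.2²/(2 × 10²) = 0.66. Assumed: the correlation ρ between mediator change and FSFI change; a carry-over of 0.6 from T2 to 3-month FSFI; a residual SD of 5 at 3 months; and no effect of the mediator on FSFI.

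**3. Spurious effect in closed form.** With mediator change in SD units:

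- Variance of T2 FSFI given arm and baseline: V = 100 × (1 − 0.6638²) = 55.9.
- Arm to mediator: a = ρ × effect/8.2.
- Mediator to 3-month FSFI, T2 FSFI omitted: b = 0.6 × (ρV/8.2) / (ρ²V/8.2² + 1 − ρ²).

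For ρ = 0.5 and a 5-point effect, a = 0.305 and b = 0.6 × 3.41/0.958 = 2.14. The indirect effect is 0.305 × 2.14 = 0.65 points. The total effect is 0.6 × 5 = 3.0, so about 22% appears mediated when nothing is. For ρ = 0.3 the share is about 8%. Once T2 FSFI is in the outcome equation, the true coefficient on the mediator is zero.

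**4. How often mediation is falsely declared.** There were 2,000 simulated trials per setting. Mediation was declared when both paths had p < 0.05 and their product was positive. Both models include baseline FSFI and the baseline mediator, which is more than section 13.5 names.

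| T2 effect | ρ | T2 FSFI omitted | T2 FSFI included |
|---|---|---|---|
| 5 | 0 | 0.1% | 0.1% |
| 5 | 0.3 | 4.4% | 0.2% |
| 5 | 0.5 | 26.6% | 1.1% |
| 10.7 | 0 | 0.1% | 0.1% |
| 10.7 | 0.3 | 19.1% | 1.8% |
| 10.7 | 0.5 | 73.5% | 2.4% |

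If IE also raises the mediator directly, by an assumed 0.5 SD, the omitted-model rates are 36.3% and 83.3% (5 points; ρ 0.3 and 0.5) and 41.3% and 86.7% (10.7 points). With T2 FSFI included they are about 2%.

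Writing the coupling instead as mediator units per 10 FSFI points gives similar results. From 0.1 to 0.5 with n = 92, the rates run from 0.1% to 24% (5 points) and from 0.5% to 72% (10.7 points). With n = 96 and an assumed T2-to-3-month slope of 0.75, they are 6.3% and 26.7% at 5 points (coupling 0.3 and 0.5) and 23.0% and 77.5% at 10.7 points.

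**5. The opposite truth.** Now let mediation be entirely real and run IE → mediator → T2 FSFI → 3-month FSFI. The assumptions are n = 96, slope 0.75, mediator raised 0.5 to 1.0 units, and 3 to 8 FSFI points per unit. The planned model detects this in 59–100% of trials, and the model with T2 FSFI in 1.5–5%. A separate run gave 52–100% and 4–5%.

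**The case against.** The strongest objection is to treating T2 FSFI as a plain covariate. If the intervention theory is right, skills taught over four sessions should already have improved function by T2. T2 FSFI then lies on the causal path, and adjusting for it removes the effect Aim 3 seeks. Step 5 bears this out: the adjusted model's low positive rate is much the same whether mediation is absent or runs wholly through T2 FSFI. T2 FSFI is also affected by treatment, so ordinary regression adjustment does not identify natural indirect effects. This stands. It rules out making persistence after adjustment a condition for declaring mediation. The adjusted model is not uninformative, however. In one set of simulations where the mediator also kept a direct effect on 3-month FSFI, detection was 60% without and 59% with T2 FSFI.

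Second, the error rates rest on a coupling and an FSFI persistence that the documents do not give. With weak coupling there is no inflation, and the highest rates need strong coupling together with either the full pilot effect or a direct effect of IE on the mediator. This also stands. A reader might infer that the false-positive rate is necessarily far above 5%; the documents do not support that.

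Third, a reader might infer that the plan excludes T2 FSFI. It does not: the list in section 13.5 is open. But an open list does not commit the analyst either way, and this one choice can decide the conclusion.

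**Conclusion.** The point holds as one of identification. Mediator change and FSFI change to T2 come from the same surveys, the plan does not commit to T2 FSFI in the model, and no reverse-direction or sensitivity analysis is planned. A significant indirect effect would therefore be compatible with either direction. That conclusion does not depend on the simulation inputs.

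The size does. If better function raises the mediator and the mediator does nothing, false mediation with a 5-point T2 effect runs from under 1% (coupling 0.1 per 10 points) through about 5% (0.3) to about 25% (0.5). With 10.7 points it runs from under 1% through about 20% to about 75%. A direct effect of IE on the mediator would raise these rates.

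A reader might also infer that an indirect effect which vanishes after adjustment refutes mediation. It would not, because true mediation acting wholly through T2 FSFI was detected in at most about 5% of simulated trials after adjustment. Aim 3 is a secondary aim; the primary analysis and the 82% power are untouched.

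**What to change.** Keep the planned section 13.5 model and pre-specify the following for each mediator.

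- Name baseline FSFI and the baseline mediator as covariates, and replace the open list with a closed one.
- Add a sensitivity model with T2 FSFI in the outcome equation. Preferably use a method suited to a confounder affected by treatment, such as interventional indirect effects or a cross-lagged structural equation model. Because the mediators are not collected after T2, the cross-lagged model cannot estimate a path from T2 FSFI to a later mediator value.
- Report the two indirect effects side by side as bracketing readings. If the effect persists with T2 FSFI, that supports a mediator effect beyond the function already gained by T2. If it disappears, state that direction cannot be established, not that mediation is refuted.
- Describe a positive Aim 3 result as consistent with mediation rather than as demonstrating it.

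The cost is SAP wording and one extra model per mediator, using data already collected. The downside is a more cautious Aim 3 conclusion. No analysis of same-survey data can fully order the two changes.
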